HbA1c (Note: value does not have to be 7.5-11% at time of baseline visit)	X						X

	X	X	X	X	X	X	X
Hypoglycemia Reporting Questionnaire							
MyPlan post-hoc qualitative evaluation							X
Anthropometrics				X ¹			
Height							
Weight	X						X
Demographics and Health History	X						X
 Process Measures							
SMART Goals set, Goals Achieved/Points received, Behavioral strategies delivered, Fidelity checklist, Behavior Change Techniques	X	X	X	X	X	X	
MyPlan post-hoc qualitative evaluation							X

* baseline assessed at Week 4 (1 week after being introduced to eating plan)

1. self-report weight at midpoint to ensure no significant loss (Week 14)

8a. Primary Outcomes

Time in range

We will compare participants' average TIR during the blinded CGM wear time at baseline (0-2 week run-in period before the active intervention period) when participants will be following their usual diet to their TIR at 22-24 weeks of the active intervention period. TIR can capture the impact of short term behavior change and allows for blood glucose fluctuations to be compared between days and weeks instead of months.⁹⁷ Because 24-hour dietary recalls will be administered during the time the CGM is worn at 0-2 and 22-24 weeks, in exploratory analyses we can examine the difference in participants' alignment to the prescribed eating behavior pattern at 22-24 vs. 0-2 weeks alongside the difference in TIR at 22-24 vs. 0-2 weeks using the matched two days of 24-hour recall and CGM data pre vs. post intervention.

The 24-hour dietary recalls will be obtained by trained staff certified from the NIH/NIDDK-funded UNC Nutrition Obesity Research Center (P30DK056350; MPI [name]) using the Nutrient Data System for Research software and the multiple pass interviewing method.^{98,99} It is possible that the eating behavior pattern participants follow during the intervention will affect glycemic control differently during the day and night. For instance, not eating after dinner (i.e. no bedtime snack) may reduce hyperglycemia and improve TIR overnight. As such we will also examine differences in pre- and post-intervention TIR by day and night using time cut points established by international diabetes research consensus guidelines.¹⁰⁰

More detail about the unadjusted and adjusted outcome models that will be analyzed can be found in the Statistical Considerations section.

Eating behavior pattern adherence

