Power analyses are based on matched-pairs t-tests and a conservative estimate of 40 participants (alpha level of 0.05). Drawing from our previous study with a similar population to estimate the within-subject correlation, we have 80% power to detect an improvement in TIR of 10%.⁹⁴ In this previous study, the average TIR was 34.7% (SD=13.6), so this would correspond to an increase to an average of 42.5% TIR. The detectable effects are large, which is appropriate in this study that aims to assess preliminary effectiveness and acceptability to inform the design of a future fully-powered RCT of longer duration.

Outcome evaluation

Aim 1. Assess acceptability and adherence to a 6-month individualized planned eating intervention (“MyPlan”) among 40 youth with T1D.

1) Adherence:

We will calculate and report continuous and categorical overall adherence to the eating behavior pattern and adherence specific to each of the five eating behavior targets that make up the pattern (i.e. mean number of eating behavior targets met, proportion of participants who met each type of target, proportion of individuals who met 0, 1, 2, 3, 4, or 5 targets). Further exploratory modeling will be conducted to identify the contributions that adherence to each of the five individual behavioral targets make to overall adherence scores, as well as the relative magnitude of associations between adherence to each of the five individual behavioral targets and glycemic measures.

Acceptability:

- We will calculate continuous and categorical participant and guardian acceptability of the eating behavior pattern. Additional analyses include combined composite scores, exploratory modeling of demographic, clinical, and psychosocial predictors of acceptability will be conducted to inform both recruitment and targeted counseling strategies in future trials. We will assess acceptability related themes that emerge from answers to questionnaire free response items and questions posed as part of the qualitative post-hoc analysis of the intervention.

Aim 2. Compare glycemic control among adolescents with T1D at baseline and at the end of the 6month MyPlan intervention.

2) Effect on glycemic control:

We will compare continuous difference in TIR under the eating behavior pattern (22-24 weeks) vs. usual diet (0-2 weeks). We hypothesize that a) $TIR_{MyPlan \text{ eating behavior pattern}} > TIR_{\text{usual diet}}$

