- a) Matched-pairs t-tests will compare average TIR at 22-24 weeks vs. 0-2 weeks (overall and stratified by day/night)

- b) Linear regression modeling will examine whether change in overall degree of adherence (comparing the two 24-hour recall days at 22-24 weeks and two 24-hour recall days during 0-2 weeks) is associated with average change in 14 day TIR at endline vs. baseline
- c) Linear regression modeling will examine whether change in overall degree of adherence (comparing the two 24-hour recall days at 22-24 weeks and two 24-hour recall days at during 0-2 weeks) is associated with change in TIR using the two days of CGM data at 22-24 weeks and 0-2 weeks that are matched to the two 24-hour recalls collected at those time points.
- d) Exploratory linear regression modeling will assess whether the differences in TIR observed in models (a) (b) and (c) above persist after adjustment for self-management technology use (i.e., insulin pump vs. multiple daily injections, routine personal CGM use), physical activity, and other key clinical and demographic factors (i.e., age, sex, insurance status, parental education or other measure of socioeconomic status). Before including any of these factors in the model, we will examine their distributions as well as their bivariate associations with TIR to assess the magnitude, precision, and functional form of the relationship. An *a priori* ranking of the relative importance of these factors based on theory and existing literature will also inform the sequence with which we add them to the model. Changes in magnitude and precision of beta coefficients when different combinations of the variables are included in the model will also be considered in selection of the fully adjusted model.
- e) As part of the post-hoc qualitative evaluation of the MyPlan pilot intervention (detailed in a subsequent section), we will more deeply explore potential reasons underlying why the MyPlan eating behavior strategy may have improved or failed to improve participants' glycemic management to identify intervention levers for future studies. We will probe participants and staff about their perceived effectiveness of the strategy and reasons for this self-reported effectiveness via interviews and focus groups with project staff and a sub-sample of participants.

Process evaluation

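### The plan raises a possible day-versus-night difference in TIR response but plans only separate day and night t-tests, with no direct comparison of the two changes

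*Combined protocol and SAP*

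**What the plan says.** The combined protocol and SAP deals with day and night in two places.

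- **Section 8a, Time in range** gives the reason for the split: "It is possible that the eating behavior pattern participants follow during the intervention will affect glycemic control differently during the day and night". The example offered is that avoiding a bedtime snack might improve overnight TIR. The commitment that follows is that "we will also examine differences in pre- and post-intervention TIR by day and night using time cut points" taken from consensus guidelines.
- **Section 11, Aim 2, item (a)** gives the matching analysis: "Matched-pairs t-tests will compare average TIR at 22-24 weeks vs. 0-2 weeks (overall and stratified by day/night".

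The other Aim 2 items add no comparison between periods. Items (b) and (c) regress change in TIR on change in adherence. Item (d) is covariate adjustment: "Exploratory linear regression modeling will assess whether the differences in TIR observed in models (a) (b) and (c) above persist after adjustment". It names no day/night term. Item (e) is qualitative. No rule is given for interpreting the day and night tests together.

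**The concern.** The stated reason for the split is that the effect may differ between periods. Each stratified test answers another question: is this period's change zero? One significant and one non-significant result does not show that the changes differ, and two significant results do not show that they are alike.

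Every participant with CGM data in both windows supplies a day change and a night change, so the direct within-person comparison needs no new data. Without it, a report has only two p-values from which to discuss day versus night. It could describe the pattern as working overnight but not by day, or the reverse, when the underlying changes are equal.

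**Working it through.** **Inputs from the documents.** Section 11: "Power analyses are based on matched-pairs t-tests and a conservative estimate of 40 participants (alpha level of 0.05"). Sidedness is not stated, so two-sided is assumed. Section 11 also gives baseline TIR 34.7% (SD 13.6) rising to 42.5%, and says "we have 80% power to detect an improvement in TIR of 10" percent. Section 3, Aim 2 gives 6.8% as the detectable change.

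**The plan's own figure.** No power figure is given for day, night or their difference. The overall figure cannot be reproduced because the within-subject correlation is not reported. For n = 40, two-sided 0.05 and 80% power, the paired t-test needs (mean change)/(SD of change) = 0.454. Then:

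- 42.5 − 34.7 = 7.8 points, and 7.8/0.454 = 17.2
- 6.8/0.454 = 15.0
- 10/0.454 = 22.0

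The figures 6.8, 7.8 and 10 disagree with one another, which is a separate matter. The first two imply an overall SD of change of about 15 to 17, so 16 is used below.

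**Assumed, not in the documents.** SD of change 16 by day and 16 or 24 by night; correlation r between a participant's day and night changes; true changes of 0, 4 and 10 points alongside 6.8 and 7.8.

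**Hand check.** If each test has power p and r = 0, P(exactly one significant) = 2p(1 − p). At p = 0.80 this is 0.32, and at p = 0.50 it is 0.50. At 80% power per period with equal SDs, simulation gives 27% at r = 0.3, 23% at 0.5, 18% at 0.7 and 11% at 0.9.

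**Simulation.** 40,000 trials per setting, n = 40, the same true change by day and night, separate two-sided 0.05 paired t-tests. Cells show the percentage of trials with exactly one significant test, at r = 0.3 / 0.6 / 0.9. Simulation error is at most about half a point.

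| True change, both periods | Night SD 16 | Night SD 24 |
|---|---|---|
| 0 | 9 / 8 / 4 | 9 / 7 / 4 |
| 4 | 37 / 27 / 13 | 34 / 27 / 18 |
| 6.8 | 31 / 23 / 12 | 47 / 40 / 33 |
| 7.8 | 22 / 17 / 9 | 43 / 38 / 33 |
| 10 | 5 / 4 / 2 | 27 / 26 / 24 |

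A paired t-test of (night change − day change) rejected in about 5% of trials in every setting.

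**The opposite error.** Suppose the true change is 16 points by night and 8 by day, with SD 16 each. Both stratified tests are significant in 87% of trials, which could be read as the same effect in both periods. The direct test detects the difference in 74% (r = 0.3) to 93% (r = 0.6).

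**Precision of the direct comparison.** SD of the contrast = √(SD_day² + SD_night² − 2·r·SD_day·SD_night). The 80%-power detectable difference is 0.454 × SD, and the 95% CI half-width is 2.023 × SD/√40.

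| Night SD, r | SD of contrast | Detectable difference | CI half-width |
|---|---|---|---|
| 16, 0.3 | 18.9 | 8.6 | 6.1 |
| 16, 0.6 | 14.3 | 6.5 | 4.6 |
| 24, 0.3 | 24.5 | 11.1 | 7.8 |
| 24, 0.6 | 19.3 | 8.8 | 6.2 |

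Over these four settings, power is 17–41% for a true 4-point day-night difference and 40–83% for 6.8 points.

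**The case against.** - **The plan commits no error of inference.** A reader might infer that the sponsor intends to declare a day-night difference whenever one test is significant and the other is not. No passage says so. The stratified tests are valid for what they test, and the bedtime-snack example concerns night alone, which the night test addresses. The only glycemic hypothesis in section 11 is that TIR is higher under the eating pattern than under usual diet. All of this stands. What remains is that section 8a gives a differing effect as the reason for the split, and nothing planned estimates that difference.
- **The percentages depend on assumptions.** This stands. They count how often a pattern of p-values arises, and the pattern becomes an error only if it is misread. Rates above about 37% need a night SD of 24, for which the documents give no figure. In the other direction, a high correlation does not remove the problem when night is more variable: the rate is still 33% at r = 0.9 for 6.8 or 7.8 points. The 2–5% for a 10-point change holds the SD at 16. If 10 points is instead the change with 80% power (SD 22.0), the equal-SD rates of 27% at r = 0.3 and 23% at r = 0.5 apply.
- **Misdirecting the next trial.** A reader might also infer that a false day/night pattern would decide which eating targets the next trial keeps. The pilot is meant to inform that trial, but no passage makes target selection depend on the day/night result, so this is speculative.
- **The direct comparison is underpowered.** This is largely right at n = 40. It is a reason to report the CI, not to omit the comparison.

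**Conclusion.** The point holds as a gap between the stated question and the planned method. Section 8a raises a possible difference by day and night, and section 11, Aim 2(a) provides only a test within each period.

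The size is conditional. For n = 40, an equal true change of 4 to 7.8 points, SDs of 16 by day and 16 to 24 by night, and correlation 0.3 to 0.6, exactly one test is significant in about 17–47% of trials. The rate drops to about 9–13% (equal SDs, correlation 0.9), 4–9% (no effect) and 2–5% (10-point change, equal SDs of 16). The absence of a direct comparison is certain; how often it could mislead depends on SDs and correlations that the documents do not give.

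This is a worthwhile, low-cost improvement to an additional analysis in a single-arm pilot. The overall TIR comparison is not affected.

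**What to change.** In section 11, Aim 2(a), add that for each participant the night TIR change minus the day TIR change will be calculated, using the same day/night cut points as the stratified analysis, and compared with zero by a paired analysis. Label it exploratory and report the estimate with its 95% CI. State that any day-versus-night statement will rest on that CI, not on comparing the two stratified p-values, and that a CI including zero will not be read as showing equal effects. Keep the day and night changes as estimates with their own 95% CIs.

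The cost is a few sentences and one further paired analysis of data already collected, with no change to sample size or to the overall TIR test. The small downside is the limited power of the contrast at n = 40.

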Study Phases	1. Screening and Pre-Intervention Data Collection: Screening for eligibility, recruiting and obtaining consent; Collection of basic demographic, health, diabetes knowledge, eating and physical activity pattern information via

	
questionnaires at baseline visit. HbA1c, height, and weight measurements at baseline visit.
 
 2. Run-in (2 weeks): Set-up mobile device and text reminders for mobile data collection; Collection of daily logs and two 24-hour recalls to inform eating plan designed by RD; 2-week CGM wear. 3. Intervention (22 weeks): Study intervention 4. Post-Trial Data Collection: Completion of eating plan acceptability Assessment, questionnaires, 2-week CGM wear, HbA1c, height, weight measurements.
Safety Evaluations	Participants will be asked about hypoglycemic events at each study visit and support session with the RD (by phone or in-person). Participants will be instructed to contact the study endocrinologist and/or RD to report any cases of severe hypoglycemia. The RDs will communicate with the study endocrinologist to ensure that any needed insulin adjustments are made throughout the study period. Participants will be encouraged to monitor their weight at home throughout the study period. Weight and height will also be collected at baseline, 3 months, and 6 months to monitor any changes and ensure healthy maintenance of weight and growth.
Statistical and Analytic Plan	
Adherence outcome:
 
 • Planned eating adherence (primary measures): Weekday and weekend adherence to five eating behavior targets/goals that define the MyPlan strategy will be calculated continuously and categorically. Additional measures will include adherence consistency, defined as the extent to which youth performance on the adherence metrics differs between the dietary recall days, as well as proportion of completed telehealth visits/phone calls, and diet-self-monitoring days (exploratory measures). 
Acceptability outcome:
 
 • Categorical and continuous 5-item measure of acceptability (primary measures) • Additional measures include qualitative information, which will be analyzed for themes (exploratory measures). 
Glycemic outcomes:
 
 • Percent time in the glycemic range 70-180mg/dL comparing CGM wear time at baseline and 6 months (primary measure) • HbA1c (secondary measure)

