Data and Safety Monitoring Plan	Data quality and safety monitoring will occur within the research team (data quality committee). There will be an internal DSMB committee composed of [name] (Study Design and Statistical Analysis), [name] (Nutrition) and [name], PhD, MPH (Pediatric Endocrinology), in addition to our internal research team members ([name] RD; [name] PhD RD; [name]; and study manager [name], MSPH). The committee will monitor participant accrual and retention, progress, completeness of standardized measures, and attendance at intervention sessions, as well as occurrence of hypoglycemia or other adverse events. All aspects of data collection and data storage will be carefully monitored to ensure rapid detection of errors, inconsistencies or other problems. Distributions of key variables will be monitored for data quality and safety. AE and SAE, as defined by NIH, will be reported to the local site investigator and corresponding IRBs. AE/SAEs will be reviewed monthly.

1. Executive Summary

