Alignment of participant behavior to the prescribed eating behavior pattern will be objectively assessed via two unannounced 24-hour dietary recalls (1 weekday, 1 weekend per week) collected during the 0-2 week and 22-24 week CGM wear time of the MyPlan study. Adherence metrics (weekday and weekend) will include proportion of participants who followed each eating behavior target, proportion of participants who met 0-5 eating behavior targets, and average number of targets met

In exploratory analyses, participant logs and 24-hr recalls will also enable identification of which snacks/meals are most often missed, which snacks/meals deviate the most from time or carbohydrate distribution targets as specified in the planned eating plan, as well as which aspects of regular eating pose the biggest challenges to adherence. These metrics will help with targeting counseling and focusing goal-setting, as well as areas to focus the design of future trials.

Eating behavior pattern acceptability

Although acceptability of the individualized planned eating plan will be ascertained every week after the plan is introduced, acceptability will be reviewed formally at 3 months, and again at the conclusion of the intervention period. Participants and their parent/guardians will fill out an acceptability assessment that we have used in previous studies.^{101 17} We will calculate separate composite acceptability scores (5 highly acceptable, 20 highly unacceptable, >10 unacceptable) from ordinal responses to statements from an 5-item instrument designed to capture ease of eating pattern

adoption, satisfaction, food enjoyment, sustainability, and ease of blood sugar management. As part of the post-hoc qualitative evaluation of the intervention, we will conduct short semi-structured qualitative exit interviews with teenager and parent participants and project staff to ascertain barriers and facilitators to following the eating strategy, likes and dislikes, recommendations for modifications, likelihood of recommending the strategy to others, and the eating behavior target participants found most difficult to follow, alongside other feedback related to intervention design, materials, and implementation.

8b. Secondary Outcomes

HbA1c

At baseline and 26 weeks, HbA1c will be measured using point-of-care testing.

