To capture perceptions of food and body weight, as well as disordered eating behavior that may pose challenges for planned eating plan adherence, the validated Diabetes Eating Problem Survey¹⁷ will be administered to participants at baseline and at the end of the study. It is also possible that personalized eating plan may positively or negatively impact disordered eating behavior. Results from this survey, including change in survey scores throughout the study, will facilitate identification of barriers to planned eating

plans and help inform the counseling strategies and individualized eating plans given to participants.

Hypoglycemia

Severe and non-severe hypoglycemia will be defined according to recent consensus guidelines (54-70mg/dl; <54 mg/dl; requiring external assistance for recovery)¹¹. To ensure continued safety of participants and the compatibility of the planned eating plan with the participant's lifestyle, the participants will be systematically queried regarding occurrence of serious hypoglycemia, at the end of the study, and during each meeting and support call with the RD using the hypoglycemia reporting instrument that queries instances of hypoglycemia that occurred since the last session. Fear of hypoglycemia and behaviors used to manage this fear will also be assessed at baseline and the end of the study through a questionnaire in order to ascertain whether this fear is impacted at all by the predictability of the planned eating intervention that the participant is being asked to follow. In the case of any event of serious hypoglycemia in between structured meetings and calls, participants will be instructed to contact their study physician either directly, or through the RD, to determine any needed adjustments to the planned eating plan or insulin dosing.

Eating and Physical Activity Pattern

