The physical risks to adolescents in this study are the same as those that would occur as a result of routine nutrition care; however, any adverse changes in glycemic control as a result of dietary intervention will be reported to CCHMC and UNC providers and medical staff who will evaluate these cases individually. Study personnel will be trained to identify the signs and symptoms of a blood glucose level that is low or high. They will also be trained to check the blood glucose level if necessary, using a glucometer. Any youth experiencing hypo/hyperglycemia or an otherwise potentially expected symptom related to diabetes will be encouraged by study personnel to consult their diabetes care provider or to go to the emergency room immediately as needed. Local medical policies and procedures for handling adverse events in clinic will be followed. If participants experience hypoglycemia or hyperglycemia outside of study visits, they will be advised to treat these situations per their usual diabetes care plan. Participants will receive the results for study HbA1c and CGM measurements after the study. Their providers will also receive these results. Participants and their parents will be encouraged to discuss their results with their providers.

The interventionists (Registered Dietitians) and study physicians will communicate regularly (verbally and in writing per protocol) regarding glucose control so that any changes in medical management can be made in a timely fashion, as it is understood that with changes in dietary patterns, adjustments in medical management for glycemic control may be needed.

At each study visit and RD check-in call, hypoglycemia events will be reviewed with the participant. Participants will be asked to notify the study team within 48 hours of any severe hypoglycemic event (seizure, coma, or need for glucagon administration).

Psychological and social risks are expected to be minimal as previously discussed. We will briefly query use of illegal behaviors including recreational drug and alcohol use as these may impact on adherence and priorities for problem solving as relates to diabetes self management. If participants reveal information that indicates that he or she is a risk to self or others, research staff will follow local clinic site procedures, including mandated reporting. Participants will be informed, as part of the informed consent process, regarding the limitations of confidentiality.

Vulnerable Subjects

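### The DSMB is to monitor both low and high blood glucose, but the described participant queries and reporting rules ask about lows only

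*Combined protocol and SAP*

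**What the plan says.** Section 14 (Adverse Events) gives low and high blood glucose as examples of anticipated events. It says, in two places, that the DSMB will follow their occurrence.

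The collection described elsewhere concerns lows:

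- Section 12 (Protections against Risk): "At each study visit and RD check-in call, hypoglycemia events will be reviewed with the participant".
- Section 8c (Hypoglycemia) describes a "hypoglycemia reporting instrument that queries instances of hypoglycemia that occurred since the last session". It is used at each dietitian contact and at the end of the study.
- Section 12 adds a deadline: "Participants will be asked to notify the study team within 48 hours of any severe hypoglycemic event (seizure, coma, or need for glucagon administration".
- Synopsis, Safety Evaluations: "Participants will be instructed to contact the study endocrinologist and/or RD to report any cases of severe hypoglycemia".

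For highs, Sections 12 and 14 give staff training and advice to the youth. Staff learn to recognise a glucose level that is too high as well as too low. Youth are told to follow their usual care plan, see their own provider, or go to the emergency room if needed. No instruction to inform the study is attached. The text provided does not name DKA.

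**The concern.** The board is given a monitoring task in two directions, and the described questions to participants supply information in one. If nobody asks about DKA or a high that needed emergency care, and families are not told to report it, the team learns of it only when someone volunteers it or it comes up in general discussion of glucose control.

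This matters for safety because the participants are minors with a qualifying HbA1c of 7.5-11%. Their eating pattern is being changed, and Section 12 expects that medical management may need adjusting as a result. Section 8c lets a reported serious low lead to a change in the eating plan or in insulin dosing. No matching participant report is described for a serious high. At the monthly adverse event review and the mid-study DSMB meeting, a short list of high-glucose events could mean few events or few questions.

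**Working it through.** No power or sample-size arithmetic applies. The check sets the monitoring duty beside each described source of information.

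**1. Solicited routes**

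| Route | Where described | Lows | DKA or highs |
|---|---|---|---|
| Query at visits and sessions | Synopsis, Safety Evaluations | yes | no |
| Hypoglycemia questionnaire in the schedule | Section 8 table | yes | no |
| Reporting instrument | Section 8c | yes | no |
| Review at visits and calls | Section 12 | yes | no |
| Participant told to report | Synopsis, Safety Evaluations | severe | no |
| Participant told to contact the study physician between sessions | Section 8c | serious | no |
| Participant notice within 48 hours | Section 12 | severe | no |

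Queries: 4 of 4 descriptions cover lows only. Participant-to-study notification: 3 of 3 rules cover lows only.

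**2. Other routes by which a high could become known**

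- *SAE definition (Section 14).* It includes inpatient hospitalization, so a DKA admission qualifies. It classifies an event already known and does not find one.
- *Staff reporting of AEs (Section 14).* Immediate reporting is for events connected with the intervention. Staff must already know of the event and judge it connected, although the same section gives the relatedness decision to the DSMB.
- *Reporting of adverse glycemic changes (Section 12).* This covers both directions, but it runs from the study to clinic providers. No query, definition or deadline is given.
- *Dietitian-physician communication (Section 12) and the Executive Committee (Section 14).* Both may surface some events. Neither is described as asking families about them.
- *Chart review and health history.* Section 8c describes chart review at the pre-trial visit. The schedule's health history row appears to be marked at week 26 as well, but the table is broken in the text, and week 26 is too late for mid-study review.
- *Study glucose data.* The CGM is blinded. For HbA1c, "At baseline and 26 weeks, HbA1c will be measured using point-of-care testing". On feedback, "Participants will receive the results for study HbA1c and CGM measurements after the study". As described, these data do not tell the team about a clinical event while a participant is on the plan.

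**3. Three events traced through the plan**

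- *Severe low:* asked about at the next contact, and the participant is told to report it within 48 hours.
- *DKA with admission:* an SAE once known, but no described question or instruction makes it known.
- *Emergency visit for a high, no admission:* no described question or instruction. It does not meet the hospitalization criterion, so it would be an SAE only under another criterion, such as being life-threatening.

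**4. Contacts that could carry the missing question**

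Section 8 schedule, contacts that look back on time under the plan: 7 weekly (weeks 4-10) + 6 bi-weekly (weeks 12-22) + 1 last session (week 24) + 1 visit (week 26) = 15 per youth.

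Figure 3 in Section 9 agrees: 8 + 7 sessions + 1 visit = 16, less the week 3 session, which looks back on the run-in, = 15.

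Contacts are 1 to 2 weeks apart, so an added item would look back about 2 weeks at most if sessions are kept. The 15 is a count of opportunities to ask, not of events missed.

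**The case against.** The strongest reply is that highs are already inside the safety system. A DKA admission is an SAE, AEs and SAEs are reviewed monthly, adverse glycemic changes go to clinic providers, staff are trained on highs, and a committee that includes the study endocrinologists meets weekly and then bi-weekly to oversee participants' well-being. Usual diabetes care continues, and some youth may wear a personal CGM. Close attention to lows is also reasonable for a plan that spaces meals, drops the after-dinner snack and may prompt insulin changes.

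Much of this stands, and it rules out several stronger readings:

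- *That high-glucose events fall outside safety reporting.* They do not. The gap is in solicitation, and in highs treated without admission.
- *That the AE definition excludes them as anticipated.* The wording is ambiguous. It also admits events arising from the population under study, and the grading scale has a diabetes-related code.
- *That the synopsis confines the DSMB to lows.* Its list reads "as well as occurrence of hypoglycemia or other adverse events", which is open-ended, so the absence of highs there shows little.
- *That sparse study CGM measures the gap.* The CGM serves the time-in-range outcome. More blinded wear would not tell the team about an emergency visit.
- *That the forms do not ask about highs.* Neither the hypoglycemia instrument nor the session guide is reproduced. One can say only that no such question is described.

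What the reply does not supply is a described step at which participants are asked about these events or told to report them.

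**Conclusion.** The point holds as a gap in solicited safety collection. The DSMB is to follow glucose events in both directions, while 4 of 4 described queries and 3 of 3 participant reporting rules cover lows only. Followed as described, the plan would ascertain DKA and emergency-treated highs less completely than lows at the monthly review and the mid-study DSMB meeting. A low count of highs could not safely be read as few events.

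The size in events is unknown. The documents give no rate of DKA or emergency visits, and the unsolicited routes would catch some of them. The conclusion assumes that the unseen instruments ask what the protocol says they ask. If the forms already cover highs, only the protocol text needs correcting. Nothing here affects the power calculation or the analysis of time in range, HbA1c, adherence or acceptability.

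**What to change.** 1. Add about three yes/no items to the existing per-session hypoglycemia questionnaire, each for the period since the last contact: DKA or hyperglycemia needing unscheduled care; emergency visit; hospital admission.
2. Extend the 48-hour participant notification in Section 12 to DKA.
3. State in Section 14 that high-glucose events needing unscheduled care but not admission are logged even though they are anticipated. Admissions already fall under the SAE definition.
4. Show these events as a row in the DSMB's event summary.

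The items go on a form already in use, so no visit is added and the sample size does not change. The cost is a slightly longer call and more events to log and adjudicate.
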